**Epilepsy Adherence in Children and Technology (eACT): Fostering
Medication Adherence in Children With Epilepsy Using mHealth
Technology**

Clinicaltrials.gov NCT03817229

Unique Protocol ID: 2018-8411

Version 1.0-5/20/25

Power and Sample Size Estimation

Sample size estimation was informed by results of previous studies of adherence interventions. Effect sizes for education-focused adherence interventions with reminders in other chronic conditions relative to controls (e.g., treatment as usual, pre-post) range from 0.08-0.20 [42, 43], while those with adherence feedback range from 0.78-1.03 [44, 45]. Specifically, an HIV study found that individualized adherence feedback demonstrated a large, standardized effect size (Cohen's $d=0.78$) [44]. Similar and higher effect sizes have been found for mHealth interventions that include education, automated digital reminders, or individualized feedback in adult samples including asthma, diabetes, and heart disease (Cohen's $d=0.70-2.51$) [46-48].

Given the range of observed effect sizes and taking into account the size of clinically meaningful changes in adherence, sample size was determined to detect a small-to-moderate standardized effect size (Cohen's $d=0.36$) for the primary analysis of SMART Stage 1 comparing intervention to control with 80% power with significance level 0.05. Assuming 2:1 randomization to intervention vs control yields a conservative total sample size estimate of 270, with ~180 participants randomized to intervention and ~90 to control. This sample size leads to 97% power to detect a moderate standardized effect size (Cohen's $d=0.50$).

Power for the secondary analysis involving pairwise comparison of the intervention strategies embedded in the SMART is informed by effect sizes for our face-to-face problem-solving adherence intervention, which incorporates individualized adherence feedback relative to treatment as usual. These effect sizes ranged from from 0.95 (1st problem-solving session) to 1.59 (2nd problem-solving session). Power analyses for comparison of intervention strategies require additional unknown assumptions, such as the anticipated response rate to intervention at the end of Stage 1. Assuming a 50% response rate to SMART Stage 1 intervention and a Bonferroni multiplicity adjustment, the proposed sample size provides 80% power with significance level 0.05 to detect a standardized effect size of $d=0.69$ between any pair of the embedded intervention strategies #1 - #3.

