To achieve the proposed sample size, the planned study sample was 600 participants across sites, with the goal of approximately 330 of the 600 being randomized (i.e., 10% attrition during the baseline phase, and 45% would be > 95% adherent, completing the study before randomization) [5]. Following initial randomization, these ~300 participants were to be assigned in a 2:1 ratio to intervention ($n=200$) and control ($n=100$). Making a conservative assumption of 10% attrition of participants in each initial SMART intervention arm results in anticipated $n=180$ randomized to intervention and $n=90$ randomized to control at the end of Stage 1. However, per federal and institution specific guidelines, recruitment was suspended during the COVID-19 pandemic, and the study team determined that 450 participants would need to be enrolled for $n=180$ to be randomized to the intervention arm and $n=90$ randomized to the control arm.

Statistical Analysis Plan

Primary Analysis Plan:

An intent to treat approach will be undertaken for all analyses, and a significance level of 0.05 will be used. The primary analysis examines the efficacy of the mHealth adherence intervention in caregivers of youth (ages 2-12) with newly diagnosed epilepsy (< 2 years) on electronically monitored adherence relative to control on the basis of the primary outcome of change in electronically monitored adherence from baseline, calculated using the baseline and final 30-day adherence. The primary hypothesis is that participants initially randomized to intervention will exhibit significantly greater improvements in adherence compared to those randomized to control from baseline to end of Stage 1. Although sample size was calculated conservatively based on use of a two-sided, two-sample t -test with unequal sample sizes, to achieve a more efficient analysis with enhanced power, the primary analysis will be based on a standard analysis of covariance with adherence at the end of Stage 1 as the dependent variable and baseline adherence as the covariate.

Secondary Analysis Plan:

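### The SAP's sample-size figures do not fit together: 450 enrolled for 180 and 90 randomized has no stated yield and no Stage 1 loss allowance

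*SAP*

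**What the plan says.** All of this is in the SAP, Power and Sample Size Estimation, unless noted.

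- **Sizing.** A total of 270, "with ~180 participants randomized to intervention and ~90 to control", is said to give 80% power at d=0.36 and 97% at d=0.50, at significance level 0.05. The Primary Analysis Plan says that the sizing used a two-sided two-sample t-test. Protocol 8.1 gives the same numbers.
- **Plan for 600 enrolled.** The goal was "approximately 330 of the 600 being randomized (i.e., 10% attrition during the baseline phase, and 45% would be > 95% adherent". The next sentence says "these ~300 participants were to be assigned in a 2:1 ratio to intervention" (200) and control (100). "Making a conservative assumption of 10% attrition of participants in each initial SMART intervention arm", the SAP arrives at 180 and 90, the latter described as "randomized to control at the end of Stage 1".
- **Revised plan.** After the COVID-19 suspension of recruitment, "the study team determined that 450 participants would need to be enrolled for" 180 "to be randomized to the intervention arm and" 90 to control. No randomization rate, baseline attrition or Stage 1 loss is given for this figure. The protocol (sections 1, 4 and 6) still plans 600 and does not mention 450.
- **Analysis.** According to the Primary Analysis Plan, "the primary analysis will be based on a standard analysis of covariance with adherence at the end of Stage 1 as the dependent variable"; the covariate is the baseline value. Handling of Missing Data uses complete cases, unweighted or inverse probability weighted.

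**The concern.** Two adjacent sentences use the same pair of numbers for different things. In the plan for 600, 180 and 90 are what remains after Stage 1 loss. In the revised plan they are, as worded, the number randomized. A participant lost in Stage 1 contributes no outcome under either complete-case analysis, so the difference bears directly on power.

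The step from 450 to 270 also cannot be reproduced. A suspension of recruitment explains slower enrolment, but it does not by itself explain why a larger share of enrolled families would be randomized. The reader therefore cannot tell which number the stated 80% power belongs to. That matters most if the result is null or borderline near d=0.36, the effect on which the trial was sized.

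**Working it through.** **Inputs.** From the SAP: two-sided alpha 0.05; d=0.36 and d=0.50; 2:1 allocation; 180:90 for the stated power; 10% loss per arm in Stage 1; 10% attrition in the baseline period; 45% above 95% adherent; 600 and 450 enrolled.

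**1. Reproduce the stated power.** For the t-test, the noncentrality is d × √(n1·n2/(n1+n2)), with n1+n2−2 degrees of freedom.
- 180:90: √(180×90/270) = √60 = 7.746. At d=0.36 the noncentrality is 2.789 and power is 79.4% (stated 80%). At d=0.50 it is 3.873 and power is 97.1% (stated 97%). The effect detectable with 80% power is d=0.363.

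The stated figures are reproduced, and they belong to 180:90 analysed.

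**2. Yield in the plan for 600.**
- Sequential rates: 600 × 0.90 × 0.55 = 297, which matches the ~300 used afterwards; 300 × 0.90 = 270.
- 600 × 0.55 = 330. The 330 therefore leaves out the 10% baseline attrition named in the same sentence.

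**3. Yield needed and available from 450.**
- Needed for 270 randomized: 270/450 = 60.0%.
- Needed for 270 evaluable after 10% loss: 270/0.90 = 300 randomized, and 300/450 = 66.7%.
- Stated rates, sequential: 0.90 × 0.55 = 49.5%, so 450 × 0.495 = 222.75, about 223.
- Stated rates, both taken as shares of those enrolled: 450 × (1 − 0.10 − 0.45) = 202.5.
- Adherence rate only: 450 × 0.55 = 247.5.

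No way of combining the two rates gives 270 from 450.

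**4. Power if 180 and 90 are literally the numbers randomized and 10% are lost in Stage 1.**
- Evaluable: 180 × 0.90 = 162 and 90 × 0.90 = 81.
- √(162×81/243) = √54 = 7.348. At d=0.36 the noncentrality is 2.645 and power is 75.0%. At d=0.50 it is 3.674 and power is 95.5%. The detectable d at 80% power is 0.383.

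**5. The planned analysis of covariance at 162:81.** The SAP gives neither the correlation between baseline and end-of-Stage-1 adherence (rho) nor the SD on which d is scaled, so both are assumed here, with equal variances at the two times. The residual variance is multiplied by (1+rho)/2 relative to the change-score variance, or by 1−rho² relative to the end-of-Stage-1 variance; degrees of freedom are n−3. Power at d=0.36:
- rho 0.3: 90.5% (d on the change SD) or 78.9% (d on the end SD)
- rho 0.5: 86.1% on both
- rho 0.7: 81.5% or 95.8%

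Power is at least 80% for rho up to about 0.77 on the change SD and from about 0.34 on the end SD. Both scales therefore reach 80% for rho of about 0.34 to 0.77.

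**The case against.** The strongest reply is that the SAP uses the word randomized loosely. The sentence just before the 450 figure applies it to counts taken after attrition, and the sizing paragraph applies it to the 180 and 90 that reproduce the stated power, which are analysed numbers. On that reading no allowance is dropped and power stays near 80%. This is a fair reading, and it is why a reader who infers that power is simply 75% goes too far. It does not remove the problem: 300 of 450 must then be randomized, 66.7% against a stated 49.5%, and the revised sentence lacks the end-of-Stage-1 qualifier.

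The second reply is that 75% is not the power of the planned primary analysis. That also stands. The t-test was the deliberately conservative basis for sizing, and the analysis of covariance reaches 80% over a wide middle range of correlations. The SAP also calls its 10% loss conservative; at an assumed 5% loss (171:86) the t-test has about 77% power. These replies limit the consequence, but the stated 80% and 97% remain t-test figures and should match the number analysed.

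Third, the 10% and 45% rates belong to the plan for 600. A reader might infer that 450 enrolled left only about 223 randomized, with t-test power near 71%, or 67% after Stage 1 loss. The documents do not support that: they do not say that those rates still applied when 450 was set, and observed rates may lie behind it.

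**Conclusion.** The figures are wrong as written, and the point is minor. On either reading they do not fit together. Taken literally, the revised target loses the attrition allowance on which the stated power rests. Taken loosely, it needs a yield well above the only one that the SAP gives. The figure of 330 contradicts the attrition in its own sentence.

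The loss of power is conditional on three things: that 180 and 90 are randomized counts, that the full 10% are lost in Stage 1, and that the t-test is the reference. Under those conditions it is about 4 points at d=0.36 (79.4% to 75.0%) and under 2 points at d=0.50 (97.1% to 95.5%), with detectable d moving from 0.363 to 0.383. At d=0.78, the lowest effect that the SAP cites for adherence feedback, power at 162:81 is still above 99%. Neither a shortfall in the trial nor inadequate power for the analysis of covariance is shown.

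**What to change.** Revise the text of the SAP's Power and Sample Size Estimation section:

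1. Give the randomization and attrition rates, observed or assumed, behind 450. If there are none, report the yield of 450 on the stated rates.
2. Say whether 180 and 90 are numbers randomized or numbers evaluable at the end of Stage 1, and use one term throughout.
3. Restate power and detectable d for the evaluable number (162:81 if 270 are randomized with 10% loss), for the t-test and, with a stated correlation and SD scale, for the analysis of covariance.
4. Correct 330 to about 300.

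No added enrolment and no change to the design or analysis is needed. The only downside is that the stated power may become slightly less favourable. If observed rates and an evaluable target lie behind 450, one or two sentences settle the first two items.

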individualized adherence feedback is critical to the success of this type of intervention. For example, an HIV adherence intervention study that provided electronically-monitored adherence feedback to non-adherent patients (< 95%) found a 10% improvement (i.e., 86.8% to 96.5%) in the treatment group versus 1% improvement (83.8% to 84.5%) in the control group.⁷² Interventions using individualized feedback in pediatric asthma have also resulted in short-term adherence improvements.^{73,74} Several adult studies have demonstrated significant improvements in adherence relative to control conditions with the provision of individualized adherence feedback,⁷⁵ suggesting this is a beneficial method to improve adherence in caregivers of children with epilepsy.

Problem-solving: Beyond forgetting, caregivers of children with epilepsy identify general barriers, including competing extracurricular activities, difficulty swallowing pills, and poor family communication, as well as epilepsy-specific barriers such as AED side effects and the stigma associated with having epilepsy and taking AEDs.⁵⁹ Tailored problem-solving around these more complex adherence barriers can be provided to children with epilepsy and their caregivers who most need it. For example, if caregivers report oppositional behaviors as a primary barrier, problem-solving would focus on identifying solutions, such as giving rewards for taking AEDs, to reduce oppositional behaviors. Our intervention studies demonstrate that face-to-face problem-solving is efficacious in improving adherence but does not reach many families with children with epilepsy. Thus, one goal of this proposal is to translate problem-solving content into a mHealth module with therapist-guided telehealth sessions. These problem-solving sessions require trained professionals; thus, this component is reserved for participants who are non-responsive to the initial, less time-intensive and costly adherence intervention dose (e.g., automated digital reminders, individualized adherence feedback) and need stepped-up, tailored care. Because clinician time is not required for the initial intervention, our intervention has considerable potential for sustainability and broad dissemination for epilepsy and other chronic conditions.

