The data collected will provide a rich resource for exploratory analyses investigating participant baseline characteristics and post-randomization characteristics ascertained prior to assessment of Stage 1 adherence status that can inform tailored selection of initial intervention (intervention or control) and of subsequent intervention for non-adherent individuals receiving initial intervention (continue intervention or augment intervention with problem solving). We will use standard methods to evaluate whether baseline characteristics moderate participants' adherence status following initial intervention, including tests for qualitative interactions. Evaluation of moderators of outcomes at Stage 2 and at 1-, 6-, and 12-months post-intervention is complicated by the sequential nature of the interventions, requiring the use of specialized statistical methods, such as Q-learning and value-search estimation. We will also use these methods to estimate an optimal adaptive intervention strategy for individualizing selection of initial intervention and intervention in the case of non-adherence based on baseline and evolving child/family characteristics, informing strategies for future study.

Handling of Missing Data:

Missing change in adherence outcomes in the primary analysis will be addressed in several ways. Under the assumption that the adherence outcomes are exactly normally distributed and linearly related, the analysis of covariance based on the complete cases will yield valid inferences under the assumption of missing at random (MAR). To evaluate the evidence in the data under MAR without making the restrictive assumptions of normality and linearity, we will conduct the complete case analysis if missingness is nondifferential by Stage 1 assignment and less than 10% in each assignment group. To assess sensitivity of this analysis to missingness, under the assumption of MAR, we will also conduct an inverse probability weighted complete case analysis of covariance in which outcomes are weighted by the reciprocal of the estimated probability not dropping out of the study in Stage 1 based on a

logistic regression model that incorporates baseline variables associated with failure to complete Stage 1.

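### The primary ANCOVA names no variance estimator; with 2:1 allocation and a 100% ceiling, the usual pooled standard error can be too small or too large, so a robust one should be prespecified

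*SAP*

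**What the plan says.** The SAP (Primary Analysis Plan) sized the trial "based on use of a two-sided, two-sample t -test with unequal sample sizes" but analyses it differently: "the primary analysis will be based on a standard analysis of covariance with adherence at the end of Stage 1 as the dependent variable", adjusting for baseline adherence, and "a significance level of 0.05 will be used".

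The SAP (Power and Sample Size Estimation) computes the total of 270 "Assuming 2:1 randomization to intervention vs control", that is, about 180 and 90. These are the numbers left after 10% attrition from 200 and 100.

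The protocol (section 8.2, Aim 1) puts adherence on a 0-100% scale, and its Abstract and section 8 randomize only families at or below 95% at baseline.

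The SAP (Handling of Missing Data) adds an "inverse probability weighted complete case analysis of covariance" as a sensitivity analysis, with weights from a logistic model for completing Stage 1. That section calls normality and linearity restrictive, but only in connection with missing outcomes.

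Neither document mentions unequal variances between arms or names a robust, sandwich or bootstrap standard error for either ANCOVA. Neither gives an SD of adherence, a variance by arm or a baseline-outcome correlation.

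**The concern.** With equal arms, pooling the residual variance does little harm to the standard error of a treatment difference. With 2:1 allocation it matters, because the pooled variance is dominated by the larger arm while the true variance of the difference is dominated by the smaller one. If the larger arm is the less variable one, the pooled standard error is too small.

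A ceiling can produce that pattern when treatment works. In the protocol's Background, a feedback study in HIV "found a 10% improvement (i.e., 86.8% to 96.5%) in the treatment group versus 1% improvement (83.8% to 84.5%) in the control group". A treated group averaging 96.5% has little room left to vary upward.

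The stake is the confidence interval for the primary effect, which could be somewhat too narrow. The opposite is also possible. If some caregivers improve a lot and others not at all, the intervention arm can be the more variable one, and the pooled interval is then too wide.

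**Working it through.** **The plan's own figure.** Inputs from the SAP: two-sided 0.05, 80% power, d = 0.36, 2:1 allocation. Control n = (1.960 + 0.842)² × (1 + 1/2) / 0.36² = 7.85 × 1.5 / 0.1296 = 90.8, so 91, and 273 in all against 270 stated. At 180:90 the SE of d is sqrt(1/180 + 1/90) = 0.1291. Power at d = 0.36 is Φ(0.36/0.1291 − 1.96) = Φ(0.83) = 79.6% (stated 80%). At d = 0.50 it is Φ(3.87 − 1.96) = 97.2% (stated 97%). The sizing reproduces, and it assumes equal variances.

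**Closed form.** Let r be the residual variance in the intervention arm divided by that in the control arm, σ² the control variance, and the slopes equal. At 180:90:

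- Pooled SE² = [(2r + 1)/3] σ² × (1/180 + 1/90) = (1 + 2r) σ²/180.
- True SE² = rσ²/180 + σ²/90 = (2 + r) σ²/180.
- Pooled SE / true SE = sqrt((1 + 2r)/(2 + r)). Coverage is 2Φ(1.96 × ratio) − 1.

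| r | SE ratio | Coverage of 95% CI |
|---|---|---|
| 0.5 | 0.894 | 92.0% |
| 0.7 | 0.943 | 93.5% |
| 0.9 | 0.983 | 94.6% |
| 1.0 | 1.000 | 95.0% |
| 1.2 | 1.031 | 95.7% |

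With equal arms the same algebra gives exactly 1 for any r, so the unequal allocation is essential.

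**What r might be.** The documents do not say, so it was simulated: ANCOVA at 180:90, baseline at or below 95%, outcome capped at 100%, effect calibrated to d = 0.36. Assumed ranges: control mean 57-85%, control SD 13-26 points, baseline-outcome correlation 0.5; clipped-normal and left-skewed beta distributions; 6,000 to 30,000 replicates per setting. Monte Carlo error on the SE ratios is about 1-2% in the 6,000-replicate runs. Here r is the ratio of total variances.

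| How the effect arises | r | Model SE / true SE | Coverage, model SE |
|---|---|---|---|
| Everyone closes the same share of the gap to 100% | 0.48-0.67 | 0.88-0.92 | 91.5-93.1% |
| Constant shift, cut off at 100% | 0.80-0.93 | 0.95-0.98 | 93.8-94.8% |
| Some respond and others do not, or the shift varies | 0.76-1.24 | 0.97-1.06 | 94.2-96.2% |
| No effect, identical arms | 1 | 0.98-1.00 | type I error 4.8-5.6% |

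The first row agrees with the closed form: in one beta setting r = 0.55 gives sqrt(2.1/2.55) = 0.907, against 0.905 simulated. The same setting at 135:135 gave 1.00. At d = 0.50 (r = 0.43) its ratio fell to 0.878 and coverage to 91.5%, so the shortfall grows with the effect.

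A different family (logit-normal, d about 0.36) gave 0.93-0.96 for a constant latent shift, 0.95-0.99 when half the caregivers respond, and 1.01-1.05 for a varying latent shift. All lie inside the range above.

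**What the robust SE does.** In the first row HC2 and HC3 bring coverage back to 94.3-95.1%. Under identical arms HC3 type I error was 4.8-5.5%; HC0 was slightly liberal at 5.1-5.9%.

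**The case against.** Four objections have force.

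1. A reader might infer that the ceiling and the design effect together force the standard error to be too small. They do not. A 0-100% bound and d = 0.36 leave the variance ratio open, and simulated ratios reach 1.06. The documents themselves expect uneven response: the protocol's Background says that improvement depended on the family's barriers, and the SAP assumes a 50% Stage 1 response rate. This stands, and it makes the point conditional.

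2. The HIV example is weak support at d = 0.36. The protocol gives means without SDs. The SAP attaches d = 0.78 to an HIV feedback study, about twice the design effect (0.78/0.36 = 2.2). In this trial the control arm also receives education and reminders, so both arms may move toward the ceiling. This stands too. The example shows that the ceiling can be reached, not what r will be.

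3. A reader might infer an inflated false-positive rate. When the arms have identical distributions r = 1, and the simulated rate is about 5%. Unequal variances alone also do not imply inflation, since a more variable intervention arm makes the test conservative.

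4. A reader might infer that the weighted ANCOVA will treat inverse probability weights as precision weights. The SAP does not say so. It describes how outcomes are weighted and leaves the variance method unstated, and this is a sensitivity analysis.

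What survives is the omission. Reading standard as pooled-variance is an inference from convention, but it is the ordinary reading, and nothing in the SAP displaces it. Uncertainty about the direction of the error argues for a robust estimator, which is approximately right either way.

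**Conclusion.** The plan leaves the standard error of its primary effect to convention, in a design where the conventional choice can be wrong in either direction. At d = 0.36 and 180:90 the model SE runs from about 12% too small to about 6% too large, with interval coverage from about 91.5% to 96.2%. The low end needs an effect that compresses the whole intervention arm toward 100%. A simple shift costs only 2-5% of the SE, and uneven response removes or reverses the error.

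All of these figures rest on assumed means, SDs, correlation and response mechanisms, because the documents supply none. The existence of the gap is certain; confidence in its size is moderate and the severity is modest. It concerns the confidence interval for the primary effect, not the sample size or the type I error under identical arms.

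**What to change.** In the SAP's Primary Analysis Plan, keep the ANCOVA and state that its standard error, confidence interval and p-value use a heteroscedasticity-consistent estimator, HC3 (or HC2). Name the version, since HC0 ran slightly liberal. In Handling of Missing Data, state that the inverse probability weighted ANCOVA uses a sandwich or bootstrap variance that accounts for the weights being estimated.

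This takes two sentences and a software option, with no new data and no change to the estimate. It should be fixed before outcomes are compared by arm, so that the estimator is not chosen after seeing results.

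It is not entirely free. Where the model SE was too small, nominal power falls by about 1 to 5 points (with HC2, for example, 86.6% to 82.8% and 85.6% to 80.7% under proportional gap closing). That power came from an understated SE, and the baseline adjustment kept simulated power at about 78% or more at the assumed correlation of 0.5. With a shift cut off at 100% the change was within about 1 point. With uneven response power was about unchanged or up to 3 points higher.

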Secondary analyses will compare the mean outcomes associated with each of intervention strategies #1 - #3 embedded in the SMART on the basis of the outcomes adherence, seizure severity/frequency, HRQOL, and healthcare utilization at 1-, 6-, and 12-months post-intervention. Strategies #1 and #2 are non-adaptive intervention strategies in that intervention is not modified in accordance with Stage 1 adherence status (or any other participant characteristics), while #3 is an adaptive intervention strategy in that intervention is augmented by problem-solving in Stage 2 only under non-adherence in Stage 1. The pairwise comparison of the non-adaptive strategy #1 to the adaptive strategy #3 represents comparison of the least resource-intensive strategy (control) to the most resource-intensive strategy. Comparison of strategies #1, #2, and #3 will be carried out using specialized methods for SMART analysis based on inverse probability weighting for estimation of the mean outcome associated with a strategy that account for the fact that actual experiences of participants may be consistent with more than one strategy; for example, a participant who is randomized to intervention in Stage 1, is adherent in Stage 1 (i.e., is a responder to intervention), and continues to receive intervention in Stage 2 is consistent with having followed either embedded strategy #2 or #3. In this case, a participant's data contributes to assessment of improvement in outcome for both strategies. For each strategy, the inverse probability weighting is by the reciprocal of the estimated probability that a participant's experience is consistent with the strategy. We will conduct pairwise comparisons of the three embedded strategies using these methods based on adherence, seizure severity/frequency, HRQOL, and healthcare utilization at 1, 6-, and 12-months post-intervention. We will also conduct a global test of the null hypothesis that the mean outcomes associated with the three strategies are the same versus the alternative that at least one mean differs from the others.

Exploratory Analysis Plan:

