For the secondary analyses, Stage 2 and later outcomes will be assumed to be missing according to a MAR mechanism. If the extent of missingness is less than 10% for each strategy, we will conduct complete case analyses comparing the embedded intervention strategies. To assess sensitivity of these analyses to missingness and to obtain a definitive analysis if the extent of missingness is greater than 10%, under the MAR assumption, we will use inverse probability weighting of complete cases in estimation of the mean outcomes associated with each strategy, where the outcomes are weighted by the reciprocal of the estimated probability not dropping out of the study/having the outcome observed as a function of baseline and previously observed variables based on logistic regression.

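### Below 10% missingness the SAP compares the embedded strategies by complete cases, which its own missing-at-random assumption does not justify; the weighted analysis it already specifies should lead throughout

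*SAP*

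**What the plan says.** The SAP's section on handling of missing data sets the assumption for the secondary analyses: "Stage 2 and later outcomes will be assumed to be missing according to a MAR mechanism". The rule follows: "If the extent of missingness is less than 10% for each strategy, we will conduct complete case analyses comparing the embedded intervention strategies". Inverse probability weighting of complete cases has two roles. It checks sensitivity, and it serves "to obtain a definitive analysis if the extent of missingness is greater than 10%, under the MAR assumption". Its weights come from the "estimated probability not dropping out of the study/having the outcome observed as a function of baseline and previously observed variables".

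The Secondary Analysis Plan defines the underlying strategy estimator: "For each strategy, the inverse probability weighting is by the reciprocal of the estimated probability that a participant's experience is consistent with the strategy". It names no covariate adjustment and no weight for being observed.

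The same missing-data section argues that complete cases are valid only for the primary analysis: "Under the assumption that the adherence outcomes are exactly normally distributed and linearly related, the analysis of covariance based on the complete cases" is said to be valid under missing at random. Even there, the complete-case analysis is allowed only if loss does not differ by Stage 1 arm and is below 10% in each arm. The secondary rule keeps the 10% limit and omits the condition on differential loss.

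On the expected amount of loss, the sample size section has: "Making a conservative assumption of 10% attrition of participants in each initial SMART intervention arm".

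**The concern.** Missing at random, as the SAP uses it, lets the chance of being observed depend on earlier adherence. A strategy mean weighted only for consistency with the strategy does not condition on earlier adherence. If less adherent families are lost more often, those who remain are not representative, and the mean shifts at any rate of loss. A 10% limit makes the shift smaller but does not remove it. The primary ANCOVA conditions on baseline adherence, so the argument made for it does not carry over.

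At stake is which Aim 2 result leads. Below the limit, the analysis that matches the stated assumption takes second place. The limit also makes the estimator depend on the data, so it can differ between outcomes and time points. Missingness of exactly 10% falls under neither branch.

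**Working it through.** **Plan's own figures.** The SAP has a sample "with ~180 participants randomized to intervention and ~90 to control". With 90 controls and 2:1 allocation, a two-sided 5% test has 79.6% power at d = 0.36 and 97.2% at d = 0.50, which matches the stated 80% and 97%. For d = 0.69, 50% non-response among 180 leaves 90. An assumed 1:1 split gives 45 against 45, and alpha is 0.05/3. Power is then 81.0% (normal) or 79.5% (noncentral t), which matches 80%. The documents give no figure for bias from missing data, so the inputs for that are assumptions.

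**Bias in closed form.** Bias of a complete-case mean = fraction missing × (mean of observed − mean of missing). The bias of a contrast is the difference between two such terms. Take just under 10% missing in one strategy and no bias in the other:

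- gap 0.5 SD: 0.0999 × 0.5 = 0.05 SD
- gap 1.0 SD: 0.0999 × 1.0 = 0.10 SD

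**Effect on the test of #3 against #1.** Strategy #3 uses 90 responders (weight 1) and 45 stepped-up non-responders (weight 2). The effective size is (90 + 90)² / (90 + 4 × 45) = 32,400/270 = 120. The standard error is √(1/90 + 1/120) = 0.139 SD.

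| Bias | Bias/SE | Rejection at nominal 5% | at nominal 1.67% |
|---|---|---|---|
| 0.05 | 0.36 | 6.5% | 2.4% |
| 0.10 | 0.72 | 11.1% | 4.8% |

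These rates apply if complete cases are always used. The SAP switches, so the rule itself has to be simulated.

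**Simulation of the rule.** Assumptions: 200 and 100 randomized, 50% response, 1:1 second randomization, equal true strategy means, and loss by Month 8 driven by Stage 1 adherence. Missingness per strategy is a raw count, and complete cases are used only if all three rates are strictly below 10%. With about 4,000 trials per scenario, the Monte Carlo error of a 5% rate is √(0.05 × 0.95/4000) = 0.3 percentage points. Slopes are log-odds of loss per SD of Stage 1 adherence. Bias is that of the complete-case contrast of #3 against #1.

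| Slope, treatment / control | Loss, treatment / control | Correlation | Complete-case bias (SD) | Rejection under the SAP's rule, nominal 5% |
|---|---|---|---|---|
| −1.0 / 0 | 10% / 10% | 0.6 | about 0.06 | 5.7% |
| −1.5 / 0 | 10% / 10% | 0.6 | 0.07–0.08 | 6.2% |
| −1.5 / 0 | 10% / 5% | 0.8 | 0.10 | about 10% |
| −1.5 / −1.0 | 10% / 10% | 0.6 | 0.02 | about 5% |
| −1.0 / −0.5 | 10% / 10% | 0.6 | 0.03 | about 5% |
| same in both arms | same | 0.6 | near 0 | about 5% |

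With 10%/5% loss, slope −1.5 in treatment only and correlation 0.6, the rule rejects 8.0%. Among trials that take the complete-case branch under one-arm dependence, rejection is about 7–11%. The weighted contrast has bias near zero in these scenarios, and its SD is 2–7% larger.

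**How often the branch is taken.** At 10% loss in both arms it is about 17% of trials if loss is unrelated to adherence and 31–36% if related. At 12% loss it is about 11%, and at 15% about 1%.

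The count matters because the SAP does not define it. Take 100 responders with 3% lost and 100 non-responders with 17% lost. Arm loss is (3 + 17)/200 = 10%. The raw rate per strategy is (3 + 8.5)/150 = 7.7%, because only half the non-responders are counted. A weighted rate would be 10%.

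**The case against.** The strongest reply is that the effect is small, conditional and already guarded against. Most of that stands.

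- Material bias needs loss to depend on adherence quite differently in the two arms. Nothing in the documents says it will, and partial similarity nearly removes the bias.
- The SAP plans 10% attrition in Stage 1 alone. If loss after Stage 1 adds to it, the branch becomes rare. It is also rarer if missingness is counted with the strategy weights: about 13% of trials at 10% adherence-related loss.
- The protocol's shortened follow-up removes the 6- and 12-month questionnaires for later enrollees. If these count as missing, weighting probably applies there and the issue is mainly at 1 month. The SAP does not say, so mixing of methods across time points is possible but not established.
- The weighted analysis is planned on both sides of the limit, so a discrepancy would be visible.
- Weighting needs a correct observation model. In one very steep dropout scenario (N = 270, correlation 0.5, true observation probabilities), the SD of the contrast rose from 0.14 to 0.21, and rejection was 2.1% at nominal 1.67%.

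The reply does not rescue the rule itself. Nothing in the SAP justifies complete-case strategy means under its own assumption, and the condition on differential loss that it sets for the primary analysis is absent where the estimator has less protection.

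A reader might infer that the SAP declares the complete-case result definitive. It does not use that word for it; the ranking follows only from the role given to weighting. A reader might also infer that Aim 2 as a whole runs at 8–11% false positives. Under the switching rule, rates that high appear only in scenarios with one-arm dependence and lower control loss.

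**Conclusion.** The rule is not consistent with the SAP's missing-at-random assumption and can produce a biased contrast. The size is modest and conditional: about 0.05–0.10 SD for #3 versus #1 if loss depends on adherence in the treatment arm only and the correlation is 0.6–0.8. For scale, the difference detectable with 80% power at alpha 0.05/3 is (2.394 + 0.842) × 0.139 = 0.45 SD for that contrast, so the bias is about 11–22% of it. Loss mechanisms and correlations are assumed, because the documents give none. This concerns secondary analyses only. It is a cheap improvement that is worth making, and it does not threaten the trial's main conclusion.

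**What to change.** In the SAP's missing-data section, delete the 10% switch for the secondary analyses. Name the inverse-probability-weighted analysis, as already specified, the main analysis for every secondary outcome and time point, and report the complete-case comparison as the sensitivity analysis. This also settles the case of exactly 10% and removes the need to define how missingness per strategy is counted.

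The cost is a small change of wording that swaps the roles of two planned analyses; no new data are needed. Standard errors were about 2–7% larger in the scenarios above, and more if dropout is very steep. The main result would then rest on a correct observation model, so the distribution of the weights should be reported with it.
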